the post-concussion symptom scale, as a subset of the Sports Concussion Assessment Tool 3,³ will be used as a method of assessing the presence and severity of symptoms. This paper-pencil symptom checklist consists of 22 symptoms with 7-point Likert scale per symptom to monitor subject's well-being. Participants will be instructed to report their current symptoms truthfully by circling symptom scores. Symptom scores will be manually transferred into an Excel spreadsheet for the future analyses. A tester or transferer will be blinded in regards to the group assignments and one's performance in other test parameters.

Blood Biomarker Assessment

The subject will be asked to lay on supine position with arm relaxed at 10-degree flexion. Antecubital vein blood draws will be performed each test session to help determine serum biomarker concentrations. A certified phlebotomist will thoroughly clean the antecubital fossa with an alcohol swab and draw 4 ml of whole blood into serum vacutainer tubes with a 21G butterfly needle. A Total of 16 ml blood for the study (4 ml x 4 time points). For non-athletic control subjects, 1 blood sample of 4 ml will be drawn. After the blood draw, the subject will use gauze to maintain direct pressure for 3 mins and Band-Aid will be provided. The whole blood will be centrifuged at 3,000 revolutions per minute for 20 minutes at 4°C after 40 mins of coagulation. The serum will then be divided and transferred into 1 mL cryovials and flash frozen and stored at -80°C in Exercise Biochemistry lab.

Ocular-Motor Assessment

The subject will then perform eye-movement task using the EYE-SYNC headset. This visual-tracking protocol has been replicated and validated in a number of concussion and sleep deprivation studies,⁴²⁻⁴⁷ however to our knowledge this study for the first time will unravel subconcussive effects. Prior to testing, a Snellen chart will be used to verify that the subject has a normal or corrected-to-normal vision (minimum 20/30). The subject will be seated in a normally lit room and stabilize the headset with two hands while the elbows placed on the desk. The visual stimulus will be presented using a 120-Hz frame rate LCD screen in the headset and binocular eye movements will be tracked by a single camera secured in the headset. The test stimulus consists of a red circular target, 0.5° diameter in a visual angle with a 0.2° black dot in the center. The target moves in a circular clockwise trajectory of 10° radius at 0.4 Hz, with the target speed corresponding to 25°/s. The entire testing sequence will last approximately 3 mins consisted of a calibration and 2 consecutive test runs. Calibration of the eye position is conducted by having the subject fixate on a target presented at eight locations on the circular path of the test stimulus and one additional fixation point at the center of the circular path. The fixation target was presented at these nine locations in a randomized order. Each of the two test runs consists of 6 cycles of circular movement corresponding to 15 s in duration per test run. The subject will be instructed as "follow the movement of the target as closely as possible."

Transcranial Magnetic Stimulation Assessment

After eye movement tasks, a subset of subjects (n=10) per group will participate in a transcranial magnetic stimulation (TMS) experiment, while the different subset of subjects (n=10) per group will participate in an electroencephalography experiment. These pilot studies are to assess subconcussive effects on neural activities. TMS will be used to assess physiological change in the primary motor cortex after subconcussive impacts. TMS works by electromagnetic induction: a current passed briefly through a coil of wire held over the scalp induces a magnetic field around the coil which, in turn, induces an electrical current in the underlying nerve cells on the surface of the brain. We will place electrodes in the hand to assess the cortical representation of an index finger muscle, first dorsal interosseous (FDI).

During TMS application, both subject's arms will be relaxed on a pillow. Subjects will wear goggles that are tracked by a Brainsight neuronavigation system, allowing us to register the subject's head to the dimensions of a reference structural MRI. The hot spot for FDI will be determined at the beginning of each session and stored in Brainsight so that all stimulations within a session are applied at the same site. TMS above a certain threshold induces current in the cortex that activates neurons within the stimulated area. This results in a muscle twitch or motor evoked potential (MEP), measured with electromyography (EMG). Electrodes will be placed over the muscle belly and tendon, with a single common ground electrode over the ulnar styloid process of the target arm. EMG recording will be amplified, band-pass filtered (10-1000 Hz), and sampled at 5000 Hz. MEP amplitude reflects the excitability of the stimulated area. The slope of the input/output (I/O) curve, computed from MEP amplitudes at a range of stimulation intensities, will be examined to determine the changes in corticospinal excitability at each time point. Including preparation steps, the TMS experiment will last approximately 15 mins.

Electroencephalography Assessment

For EEG experiment, we will employ a standard 62-channel electro-cap with Ag/AgCl electrodes mounted to measure brain waves during default resting mode. To this end, the subject will be seated with eyes closed for 10 mins to ensure at least 2-min artifact free neural activity data. The 62 channels will be collapsed into four topographical regions of interest (frontal, central, parietal, and occipital) in each hemisphere (left and right). The EEG data will be processed offline using EEGLAB 5.03 software. Including preparation steps, the EEG experiment will last 30-40 mins.

6.0 Reporting of Adverse Events or Unanticipated Problems involving Risk to Participants or Others

Reporting Adverse Events

[name]. (primary investigator) will serve as the data safety monitor. The data safety monitor will monitor adverse event data, oversee procedures designed to protect the privacy of subjects, and coordinate the reporting of the outcome of any investigation of an adverse event. In the event of an adverse event, [name] will report and cooperate with the IRB in any necessary investigation.

Adverse Events Associated with Soccer Heading

There is a risk of inducing symptoms such as headache, blurred vision, and disorientation during soccer heading testing, however ten soccer headers with mild head acceleration are commonly incorporated in soccer practice, and certainly soccer players utilize heading skill to direct a soccer ball for passing and scoring during practice and game. An average soccer player performs 500 headers over an entire season.^{30, 31} It is extremely unlikely to elicit concussion-like symptoms (headache, nausea, disorientation, blurred vision) from headings with mild head acceleration (Avg. 14.5g). The study protocol has been replicated in multiple laboratories, producing invaluable data to progress traumatic brain injury research. Moreover, our preliminary study in football players have shown that a player sustained 39 head hits with the total magnitude of 1,200g during a single practice, but with no change in symptoms.¹⁸ In order to minimize the risk of adverse events from soccer heading, we will only include soccer players who regularly play soccer and perform soccer headings.

Adverse Events Associated with Blood Draw

Complications of antecubital venous blood draws include bruising, local infection, phlebitis and injury to structures near the cubital vein. All of these complications are uncommon. To minimize these risks, [name]., (a certified phlebotomist) will perform the blood draws using single-use needles, tube holders and test tubes. The skin of the antecubital region will be cleaned with alcohol to further reduce the risks of infections. Following each blood draw the participant will remain seated while maintaining direct pressure against the site of the needle insertion. After each blood draw, the participant will be given a Band-aid to cover the puncture site. When the participant returns for each test session the certified phlebotomist will check the

puncture sites for any signs of complications (which would be referred for an additional medical examination).

Following the 48 hour post-test, the participant will be reminded to contact the research staff if they have any pain or discomfort associated with the procedure. Pain and dizziness/fainting are other potential risks associated with antecubital venous blood draws. During the blood collection, the participants will be placed in a supine position. Prior to sitting up the certified phlebotomist will talk to the participant to confirm that the individual is comfortable. Once the participant is in a seated position they will sit for a few minutes to ensure that they are not feeling dizzy or faint. Ice will be offered at the end of each testing session to minimize any pain.

Adverse Events Associated with Ocular-motor testing

During performing ocular-motor tasks, participants may experience a transient headache and dizziness. Because the ocular-motor testing runs for 15 seconds and repeated twice, we believe that it is rare to elicit symptoms in the short period of testing. Based on the large-scale normative data (n=50,000) acquired by SynkThink Inc. among sports athletes and military servicemen, no one has claimed abnormal symptom due to the ocular-motor testing.

Adverse Events Associated with Electroencephalography (EEG)

There is minimal risk associated with EEG. An EEG measures the electrical activity in the brain (brain waves) using electrodes (small metal discs or sensors) placed on the head with gel. The test is non-invasive and no potential harm in neural structure nor metabolic balance, and the test does not hurt. The gel used to put the discs on the head is sometimes sticky and the discs may scratch the scalp. There may be a slight discomfort associated with sitting still in one position for 10-20 minutes. The likelihood of participant experiencing electric discharge from the EEG equipment is extremely small. No adverse events have been reported as a result of the EEG experiment.

Adverse Events Associated with Transcranial Magnetic Stimulation (TMS)

There is minimal risk associated with TMS. In particular, we are using magnetic brain stimulation due to it being well-tolerated, versus direct electrical stimulation of the brain, which is very painful. TMS briefly activates nerve cells in a small area on the surface of the brain. The stimulator device uses the principle of 'electromagnetic induction' to produce a weak electric current on the surface of the brain. While the physical risk is almost none (assuming they have completed the TMS Checklist), there is the potential for the subject to have an adverse psychological reaction to the stimulation techniques. The possible side effects as it has been mentioned in literature are: seizure induction (rare), syncope (epiphenomenon), transient headache, transient neck pain, transient toothache, transient paresthesia, and transient hearing changes. Based on safety literatures on paired-pulse, there is no extra risk in paired pulse comparing to the single pulse. There is no reason to believe that single pulse TMS, itself, poses any hazard. Extensive use in [name] previous laboratory at Johns Hopkins School of Medicine has not resulted in any difficulties with the device that could pose a hazard to participants. TMS does not appear to pose any hazard to the brain beyond that of electric stimulation, which has been in clinical use for decades. The procedure appears to be safe and without any side effects. Some of the original subjects have been stimulated many

thousands of times. Some people may experience a mild headache from the stimulation. A headache, if it occurs, is usually mild and only lasts a few minutes beyond the end of the test. However, participants with a history of a migraine or other types of severe or frequent headaches will be excluded from the experiment.

7.0 Study Withdrawal/Discontinuation

Data collection will require subjects to participate in 4 test sessions. Subjects may withdraw from the study at any time. A subject may also be withdrawn from the research without his/her consent if, for example, he/she 1) comes to the 1st and/or 2nd day with intoxication, 2) sustained injury prior to the 1st and 2nd day, 3) self-reported sleep deprivation for the 1st and/or 2nd day, 4) sustained a head injury prior to the 1st and 2nd day. If the subject completed for example entire 1st day procedure (3 test sessions) and unable to participate in the 2nd day (4th test session), the subject will be reimbursed hourly for the 1st day.

For non-athletic control cohort, we will evaluate and account for the soccer players' baseline, which may be influenced by a history of repetitive heading and sports participation. This group will participate in a single test session that lasts approximately in 1.5 hours. During the session, blood draw (4mL, about 1 teaspoon), measure eye movements using an ocular motor headset, and measure the brain activity using transcranial magnetic stimulation and electroencephalography. A subject may be terminated for the study participation if he/she 1) comes to the test session with intoxication, 2) sustained injury between screening and the day of test session, 3) self-reported sleep deprivation on the day of test session.

8.0 Statistical Considerations

Power analysis

According to our previous studies [Kawata et al. (2016)¹⁷ and Hwang et al. (2016)³³] and preliminary findings (Fig 4), the effect size is estimated to be 0.55 and the standard deviation is approximately 0.6. To achieve a power of 0.80 with $p < 0.05$ as significance level, 18.68 subjects per group are suggested for the studies (Formula on the right). Although we did not have any drop-outs in aforementioned previous studies, the study would need 20 subjects per group to be able to interpret the data with any degree of confidence regarding the effects of subconcussive head impacts on outcome measures. Since we are recruiting 10 subjects per group for TMS and EEG for pilot studies, subsequent power analyses will be performed following data collection to determine whether we will need additional sample size or not.

$$n = \frac{Z_{\alpha} \quad Z_{1-\beta} \quad SD}{\text{Effect Size}^2} = \frac{2(1.96 + 0.8416)^2 (0.6)^2}{(0.55)^2}$$

Data analysis

Data analysis will be conducted by [name], associate professor of biostatistics and director of biostatistics counseling center. To maintain the purity of statistical analyses, [name] will be blinded to group assignments by simply given the data set indicating Group (A, B, C). However, for our statistical model of longitudinal assessment, time points (pre, 0h-post, 2h-post, 24h-post) will be revealed to [name].

Our primary interest is to identify the changes in biomarker expression, ocular-motor, and neural function after subconcussive head impacts in the heading group; hence, each parameter at post-heading time points (0h, 2h, and 24h) will be compared with pre-heading baseline. Each time point of the control groups (kicking and standing) will aid to interpret whether or not changes in the heading group are due to subconcussive impact, exercise, bodily hit, or simply a daily variation. To this end, a series of mixed effects regression models (MRM) with random intercept will be used for all aims.⁴⁸ The first MRM will focus on the within-group pattern of changes in biomarker expressions (PINCH and Tau), ocular-motor performance (smooth pursuit velocity gain, phase error, and gaze position error), neural activity (delta, theta, alpha, and beta powers), and motor cortex excitability (I/O curve) in 3 groups across the duration of the study – 4 time points. Next MRM will focus on between-group analyses on the variables (heading, kicking, standing) against changes in the biomarker levels, ocular-motor function, and neural function. Predictor variables include time, group, and time by group interaction. All analyses will be conducted with SAS and significance will be set at $p < 0.05$.

Study Endpoint

Throughout the study, we set the study endpoint based on subjects' well-being measured via symptom checklist or verbal claim to researchers. Because the mild nature of head impact, we expect to observe a subtle change in our sensitive outcome variables after soccer headers. To date, there is virtually no scientific evidence available to set study endpoints using ocular-motor, blood biomarker, and neuronal activity, we will guide the study based on symptoms, meaning that if a subject experiences any concussion-related symptoms following blood draw, soccer heading, ocular-motor testing, EEG, and TMS, his or her participation will be terminated.

Symptom

When a subject experiences any symptoms related to concussion (headache, nausea, blurred vision, disorientation, fogginess, sensitivity to light and noise, etc.), his/her participation will be terminated. However, there has been no participant thus far reported concussion-related symptoms due to soccer heading, blood draw, nor ocular-motor performance.

Blood Biomarker

Presently, there are no biomarker concentration levels that can serve as a cut-off point to diagnose concussion or subconcussion, while in more severe traumatic brain injury, astrocyte-derived biomarker (S100B and Glial Fibrillary Acidic Protein) have known to be useful in prognosis of brain injury and its outcome.⁴⁹⁻⁵¹ The proposed study tests neuron-enriched blood biomarkers (PINCH and tau proteins), where theoretically detecting these markers in the blood indicates neuronal damage in the brain. Our preliminary work on PINCH (Fig 4) illustrates that season-long exposure to subconcussive head impacts in football players induced increases in PINCH protein, while PINCH remains undetectable in 14 out of 16 players. However, there is no scientific evidence thus far demonstrating the association of PINCH/tau proteins in the blood and brain damage. The study design we employ allows us to test the ambiguous notion whether head impacts may cause the increase in PINCH and/or tau in the blood and possible association with neural activity measured via TMS and EEG.

Neuronal Activities

Altered neuronal functions will be measured via TMS and EEG. As noted in the hypotheses under Specific Aims, following subconcussive head impacts, we expect to observe a transient suppression of theta, alpha and beta waves (powers) in the frontal and occipital brain region measured via EEG, indicating temporary neuronal perturbation due to head impacts. Similarly, using TMS, we will target the M1 representation of a finger muscle at baseline and each post-heading time point to compute the input/output (I/O) curve, which reflects M1 excitability. If the subject experiences any adverse symptoms which are similar to concussion-related symptoms (headache, nausea, blurred vision, disorientation, fogginess, sensitivity to light and noise, etc.), he or she will terminate the study participation.

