Hypothesis: Subconcussive impacts will induce a significant suppression of theta, alpha and beta waves (powers) in the frontal and occipital brain region during resting default mode, compared with baseline levels.

Since subconcussive impacts induce diffuse force to the brain, rather than a focal injury like contusion,⁴ likely neuronal network is disrupted. Neuronal activity –delta, theta, alpha, beta powers– in the whole brain will be measured using electroencephalography (EEG) while resting.

Aim 4. Determine whether subconcussive head impacts induce physiological effects in primary motor cortex.

Hypothesis: Subconcussive impacts will significantly reduce primary motor cortex excitability compared with baseline levels.

To better characterize neuronal physiology after subconcussive impacts, we will employ transcranial magnetic stimulation (TMS) to detect subclinical, physiological change in the primary motor cortex (M1). Consistent with established protocol,⁴¹ we will target the M1 representation of a finger muscle at baseline and each post-heading time point to compute the input/output (I/O) curve, which reflects M1 excitability.

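### Does the 80% power figure, built on a two-group formula, leave the within-heading-group comparison and the TMS/EEG pilots without a valid sample size?

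*Protocol*

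**What the plan says.** Protocol section 8.0, Power analysis, takes its inputs from two earlier heading studies and from the football PINCH data in Fig 4: "the effect size is estimated to be 0.55 and the standard deviation is approximately 0.6". It puts them into a formula with a leading factor of 2, and concludes for a power of 0.80 and 0.05 "as significance level, 18.68 subjects per group are suggested for the studies". The plan is 20 per group in three groups.

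Under Data analysis in the same section, the main interest is the heading group: "each parameter at post-heading time points (0h, 2h, and 24h) will be compared with pre-heading baseline". The kicking and standing groups help with interpretation. A second mixed model then compares the groups: "Next MRM will focus on between-group analyses on the variables (heading, kicking, standing) against changes in the biomarker levels", with time, group and their interaction as predictors. One threshold covers everything: "All analyses will be conducted with SAS and significance will be set at" p < 0.05.

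TMS and EEG have 10 subjects per group each. Section 5.0 describes them thus: "These pilot studies are to assess subconcussive effects on neural activities". Section 8.0 adds that "subsequent power analyses will be performed following data collection to determine whether we will need additional sample size or not". Aim 4 in section 2.0 nevertheless predicts a significant result: "Subconcussive impacts will significantly reduce primary motor cortex excitability compared with baseline levels".

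**The concern.** Two things look wrong.

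First, the factor of 2 marks the formula as one for two independent groups, whereas the comparison described as the main interest is paired, before against after, in one group. The power paragraph names no outcome, time point or contrast for 0.55 and 0.6. By their titles in the reference list, the two heading studies concern near point of convergence and vestibular function, neither of which is among the outcomes under Data analysis. If the 80% does not apply to the main comparison, the study might be too small for it, and a reader could not tell what a null result means.

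Second, a power analysis made after seeing the pilot data, followed by more recruitment and a second test at 0.05 on the pooled data, would raise the false-positive rate. The protocol does not exclude this, and Aim 4 and the common threshold suggest that the pilots will be tested formally.

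**Working it through.** **Inputs (section 8.0).** Difference 0.55; SD 0.6; z = 1.96 (two-sided 0.05) and 0.8416 (80% power); 20 per group, or 10 for TMS and EEG. The protocol gives no pre-post correlation, so values of it below are assumptions. No multiplicity adjustment is applied.

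**Reproducing the plan's figure.** n = 2(1.96 + 0.8416)² × 0.6² / 0.55² = 2 × 7.849 × 0.36 / 0.3025 = 18.68 per group. This matches. Because the formula divides by the effect and multiplies by the SD, 0.55 acts as a raw difference; the standardised difference is 0.55 / 0.6 = 0.917.

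**Power at 20 per group, with 0.6 as the SD of the quantity compared (noncentral t).**
- Two groups: noncentrality 0.917 × √(20/2) = 2.90, 38 df, power 81%.
- Within the heading group: noncentrality 0.917 × √20 = 4.10, 19 df, power 97%. The required n is 7.849 × 0.36 / 0.3025 = 9.34, half of 18.68.

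On this reading the two-group contrast is the more demanding one, and a design sized for it more than covers the paired contrast.

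**If 0.6 is the SD of single measurements.**
- Two groups compared at one time point: the printed formula applies as it stands, and power is again 81%.
- Changes: SD of change = 0.6 × √(2(1 − ρ)).

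| Assumed ρ | SD of change | Power within heading group | Power, difference in change between two groups |
|---|---|---|---|
| 0 | 0.849 | 79% | 52% |
| 0.5 | 0.600 | 97% | 81% |
| 0.75 | 0.424 | >99% | 98% |

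The within-group comparison therefore stays at about 80% or more for any non-negative correlation. Only the difference in change falls clearly short, and only when ρ is below about 0.5.

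**If 0.55 were a standardised paired effect.** n = 7.849 / 0.3025 = 25.9, and power at 20 is 65%. The printed formula rules this reading out, since it scales 0.55 by the SD.

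**TMS and EEG at 10 per group.** Borrowing 0.917 gives 73% within group (noncentrality 2.90, 9 df) and 49% between two groups (noncentrality 2.05, 18 df). These figures only illustrate: the inputs do not come from TMS or EEG data, and the protocol claims no power for the pilots.

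**Extension of the pilots.** Simulated under no effect, with testing at 10 per group, extension if not significant, and retesting of pooled data at 0.05:
- adding 10 per group gives a type I error of 8.3%;
- adding 20 per group gives 8.9%.

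Other rules give other results. Extending only when the n implied by the observed effect is within an assumed cap of 20 to 40 per group, and counting only the final test, gives 3.2% to 5.2%.

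**The case for a change.** The strongest case for a change is that the only power figure in the protocol is not tied to the comparison that the protocol puts first, and that its inputs merge several outcomes into one pair of numbers. The tabulated range, 52% to above 99%, shows that the meaning of 0.6 matters. One sentence would settle it, and another would close the pooling question, at no cost in subjects.

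Part of this stands. The paragraph should ideally have said which contrast it covers, and a reader has to infer it. But an unlabelled figure is not a wrong one. The protocol plans a between-group model with group as a predictor, and the formula fits either a difference in change (0.6 as SD of change) or a difference at one time point (0.6 as SD of single values). The low end of the range needs a zero correlation between repeated measurements on the same person, which is an assumption with no support in the document. Null results will in any case be read from estimates and confidence intervals, which a relabelled planning figure does not alter.

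On the pilots, the tension between the pilot label and the predicted significance is real. The extension sentence, however, states no pooling and no retest, and sizing a later study is a natural reading for work called a pilot. How extended data would be handled is commonly left to a statistical analysis plan, which is not at hand.

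**Conclusion.** No change is needed. The 18.68 is correct. With 0.55 and 0.6 taken as mean and SD of change, 20 per group gives about 81% power between two groups and 97% within the heading group, so the design meets its stated 80% for the main comparison and for the two-group contrast. This holds if 20 per group complete and without adjustment for multiple tests. Power for a difference in change would fall clearly below 80% only if 0.6 is a single-measurement SD and the pre-post correlation is below about 0.5; the document supports neither condition.

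The missing label is a gap that an analyst fills sensibly from the formula, and filling it in writing would leave enrolment, models and conclusions as they are. The inflation to about 8-9% for TMS and EEG depends on a stopping rule that the protocol does not contain. It would become a real issue only if the pilot data were tested, extended and retested together at an unadjusted 0.05.

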When a subject who suffice inclusion criteria and free of exclusion criteria agree to participate in the study, he/she will be randomly assigned into one of three groups (heading, kicking-control, standing-control). A standardized and reliable soccer heading protocol will be used for the experiment. A triaxial accelerometer (Triax Technologies) embedded in a head-band pocket and positioned directly below the external occipital protuberance (inion) to monitor linear and rotational head accelerations. A JUGS soccer machine will be used to simulate a soccer throw-in with a standardized ball speed of 25mph across all 3 groups. The ball speed is similar to when soccer players make a long throw-in from the sideline to mid-field. Soccer players frequently perform this maneuver during practice and game. Subjects will stand approximately 40ft away from the machine to perform either the heading, kicking, or standing (Fig 5 & 6). [name] previous laboratory at Temple University has routinely employed the protocol and average linear head acceleration yielded from the header is 14.5g in which many of subconcussion studies in football and ice hockey have set a threshold of impact recording as 16g, indicating that impacts induced from our protocol are below the minimum magnitude recorded in other contact sports. Participants in the heading group perform 10 standing headers with 1 header per minute, whereas kicking control group performs 10 kicks. Standing control group will remain static while a soccer ball passes over the head. The subjects in the heading and kicking groups will be instructed to direct the ball back toward the JUGS soccer machine in the air, while the subjects in the standing group will remain static. The kicking and standing control groups will aid to

distinguish effects of subconcussive impact from exercise, bodily damage, and/or simply a daily variation of the outcome measures. The first phase of acute subconcussive effects will be measured at 0h-post heading, indicating immediate sensory perturbation and neuronal damage, followed by measurement of the second phase, 2h-post neural inflammatory response. Lastly, ocular-motor function coupled with neural activity at 24h-post heading will be measured to assess the third phase of subconcussive effects.

Procedure Outline

- 1. Email will be distributed**
- 2. Interested participants will contact PI (KK) to discuss Project**

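### The protocol makes pre/post change within the heading arm its primary comparison and does not make the planned time-by-group contrast the test from which a heading effect is concluded

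*Protocol*

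**What the plan says.** Protocol section 8.0 (Data analysis) opens with the aim: "Our primary interest is to identify the changes in biomarker expression, ocular-motor, and neural function after subconcussive head impacts in the heading group". From this it draws the comparison: "each parameter at post-heading time points (0h, 2h, and 24h) will be compared with pre-heading baseline". The next sentence starts "Each time point of the control groups (kicking and standing) will aid to interpret whether or not changes in the heading group" and lists impact, exercise, bodily hit and daily variation as the candidate explanations.

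Mixed models with a random intercept are then introduced to serve that purpose. The first describes the within-group pattern over the four time points in each of the three groups. The second is a between-group analysis, and the section adds: "Predictor variables include time, group, and time by group interaction". The contrast is therefore planned, but nothing says that it decides the question.

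Elsewhere:
- Section 5.0 (Research Design) names time alone as the independent variable.
- Section 5.0 (Soccer Heading Protocol) says that the two control groups are there to "distinguish effects of subconcussive impact from exercise, bodily damage, and/or simply a daily variation of the outcome measures".
- Section 2.0 words two hypotheses against baseline only. Aim 3 expects suppressed EEG power in the "frontal and occipital brain region during resting default mode, compared with baseline levels". Aim 4 reads: "Subconcussive impacts will significantly reduce primary motor cortex excitability compared with baseline levels".
- Section 8.0 (Power analysis) uses a two-group formula with 0.55 and 0.6, obtains 18.68 per group and plans 20. It does not say which comparison this serves.

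**The concern.** A change from baseline within one arm contains everything that happened between the two measurements: the head impacts, the physical effort, contact with the ball, repeated testing and time of day. It cannot separate them, and that is the protocol's own reason for randomising to kicking and standing. Randomisation supports a causal statement only through the difference between arms.

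As written, a trial in which all three arms shift alike meets the comparison that section 8.0 calls primary, and also the Aim 3 and Aim 4 hypotheses. If the interaction were null in the same trial, the protocol does not say which result governs the conclusion.

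**Working it through.** **Inputs.** From section 8.0 of the protocol: effect 0.55, SD 0.6, two-sided 0.05 (1.96 in the formula), power 0.80, 20 per group planned, 10 per group for TMS and EEG. Assumed, because the document does not give them: 0.6 is the SD of change, and the common drift is 0.10, 0.20 or 0.275 (the last is half of 0.55). The calculation covers one outcome at one time point with independent arms and t tests. It illustrates the planned mixed model and does not reproduce it.

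**1. The protocol's own figure.** 2(1.96 + 0.8416)² × 0.6² / 0.55² = 18.68 per group, as stated. The factor 2 belongs to a comparison of two groups. A within-arm test on the same inputs would need half, 18.68 / 2 = 9.34. The stated size thus matches the between-group contrast and not the comparison called primary.

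**2. No heading effect, same drift in every arm.** The heading pre/post test has noncentrality drift/0.6 × √20 on 19 df. Its probability of significance is p. Heading versus one control has expected difference zero, so its rate is 5% at any common drift.

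| Drift | Noncentrality | p, heading pre/post | Heading v one control |
|---|---|---|---|
| 0.10 | 0.745 | 0.109 | 0.05 |
| 0.20 | 1.491 | 0.294 | 0.05 |
| 0.275 | 2.050 | 0.494 | 0.05 |

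**3. If each control were read by its own p-value.** This is a possible reading, not a rule in the protocol. A false heading effect means that heading is significant and both controls are not, with probability p(1−p)²:
- drift 0: 0.05 × 0.95² = 0.045
- drift 0.10: 0.109 × 0.891² = 0.087
- drift 0.20: 0.294 × 0.706² = 0.147
- drift 0.275: 0.494 × 0.506² = 0.126
- drift 0.40 (p = 0.807): 0.807 × 0.193² = 0.030

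The excess over 5% therefore appears at intermediate drift and not everywhere. With a true heading effect of 0.55 added to the drift, the same reading detects it in about 88%, 79%, 50% and 26% of trials at drift 0, 0.10, 0.20 and 0.275. The contrast detects it in about 81% throughout.

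**4. Power of the contrast, SD of change 0.6.**
- One control, 20 per arm: noncentrality 0.55 / (0.6√(2/20)) = 2.90 on 38 df, power 0.806.
- Within-arm test, 20 subjects: 0.55/0.6 × √20 = 4.10 on 19 df, power 0.973.
- Both contrasts significant, 20 per arm: about 0.70, by simulation because they share the heading arm.
- One control, 10 per arm: 0.55 / (0.6√(2/10)) = 2.05 on 18 df, power 0.49.

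**5. If 0.6 is instead the SD at a single time.** The SD of change is 0.6√(2(1−ρ)) = 0.71, 0.60 or 0.46 at pre/post correlation 0.3, 0.5 or 0.7. Power for one contrast at 20 per arm is then 0.67, 0.81 or 0.95, against 0.91, 0.97 or 1.00 within arm.

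**The case against.** The strongest reply is that section 8.0 already handles this. The sentence after the pre/post comparison brings in the controls to judge what caused the change, the models are introduced for that purpose, the interaction is a listed term, and the study design figure describes a 3 × 4 design. A reader might infer from the primary comparison that no between-group analysis is planned, or that a pre/post change alone will be declared a heading effect. The text supports neither. What stands against the reply is that showing an intention to use the controls does not say how they decide, while the only comparison tied to the primary interest is the within-arm one.

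A second reply is that the choice of deciding term belongs in an analysis plan, which may exist. That would hold had the protocol been silent. It is not silent: it states a primary comparison, and that comparison cannot answer the question.

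Third, reading controls by their own p-values appears nowhere as a rule, and its error rates depend on assumed drift. This is right. At zero drift that reading is below 5% and has more power than the contrast (88% against 81%). A general claim that it inflates false effects would be too strong.

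Fourth, the TMS and EEG parts are called pilot studies, and wording against baseline may merely define the change score. This lowers the weight of the Aim 3 and 4 wording but does not remove the mismatch.

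**Conclusion.** The concern holds in this form: the protocol ties its primary interest to a within-arm comparison and leaves the planned randomised contrast without a deciding role. It should be fixed. The finding rests on the wording of section 8.0. The sample-size arithmetic is correct and in fact fits the contrast.

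The size is illustrative. Under common drift of 0.10 to 0.275 with no heading effect, the stated primary comparison is significant in about 11% to 49% of trials, against 5% for the contrast. This assumes an SD of change of 0.6 and 20 per arm; the protocol gives no drift size. The rates for the heading pre/post test take no account of the controls, so they are not the rate at which the investigators would claim an effect.

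**What to change.** In section 8.0 (Data analysis), state that a heading effect is concluded from the heading-versus-control difference in change from baseline, which is the time-by-group contrast already planned. Report within-arm changes and time courses, such as the tau pattern expected under Aim 1, as supportive.

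State what each control excludes. Heading versus kicking separates impact from exercise or bodily hit. Heading versus standing separates it from daily variation. A change should not be attributed to head impact on the standing contrast alone, because exercise would remain as an explanation.

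Word the Aim 3 and Aim 4 hypotheses in section 2.0 to match. In the power analysis, say that the two-group formula refers to this contrast.

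No new data or model is needed. The cost is power. With 0.6 as the SD of change and 20 per group, it is about 0.81 for one contrast against 0.97 for the within-arm test. If the sponsor requires both contrasts to be significant, about 0.70 should be stated. For the 10-per-group TMS and EEG work, one contrast has about 0.49, which fits its description as pilot work.
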